6.5 Discharge Assessments

- Physical examination/Vital signs
- Adverse event
- COVID-19 Assessment: If the patient has a COVID-19 test at any point after enrollment in the study, details of the test, date conducted, and outcome should be captured in the COVID-19 Assessment Log Form.
- Concomitant use of anticoagulant and antiplatelet medications

For physical examination and vital signs, refer to **Section 6.8** for further details.

6.6 90-day Follow-up Assessments

All subjects are required to have an office visit for the 90-day (± 30 days) clinical follow-up as well as echocardiographic follow-up. If a subject remains hospitalized 90 days post-

device removal, a 90-day follow-up form is still required. To aid in follow-up compliance, if necessary, an independent service (e.g. Hawthorne Effect) may be utilized to provide in-home visits for both the clinical and echocardiographic follow-up.

- Physical examination
- NYHA heart failure class
- Quality of life questionnaires (SAQ and EQ-5D-5L)
- Echocardiogram (performed per the Echocardiographic Core Laboratory Guidance with images uploaded to the Echocardiographic Core Laboratory via Bioclinica website)
- Adverse event
- COVID-19 Assessment: If the patient has a COVID-19 test at any point after enrollment in the study, details of the test, date conducted, and outcome should be captured in the COVID-19 Assessment Log Form.
- Concomitant use of anticoagulant and antiplatelet medications

For physical examination and echocardiogram, refer to **Section 6.8** for further details.

6.7 Unscheduled Visits

Additional subject visits, such as unscheduled visits, may occur as clinically warranted. The following information will be collected:

- Adverse Events
- COVID-19 Assessment: If the patient has a COVID-19 test at any point after enrollment in the study, details of the test, date conducted, and outcome should be captured in the COVID-19 Assessment Log Form.
- Concomitant use of anticoagulant and antiplatelet medications
- Details of any subsequent coronary interventions (e.g., repeat PCI or CABG), if applicable
- Any new valvular abnormalities (if suspected, an echocardiogram should be performed)

If an unscheduled visit is conducted due to a suspected ischemic cardiac event, troponin (NO high-sensitivity troponin) must be collected and ECG must be done. CK-MB is optional.

All efforts must be made to obtain follow-up information on subjects who have undergone procedures or have been treated for adverse events in a non-clinical investigation-related hospital(s).

6.8 Additional Information on Required Assessments

Neurological Assessments

In cases of suspected neurological dysfunction, appropriately trained individuals will perform standard neurological examinations and assessments. Subjects who exhibit signs/symptoms of cerebrovascular accident (CVA) or transient ischemic attack (TIA) should have a diagnosis confirmed by appropriate diagnostic imaging.

Echocardiographic Assessments

All subjects will have echocardiograms performed at the following time points:

- 1) Baseline – performed within 60 days prior to the index procedure; required for the analysis of the primary endpoint component (change in aortic insufficiency from baseline to 90 days) and the descriptive endpoints as well as for the assessment of the eligibility requirements (e.g. LVEF <50%, no moderate or severe aortic insufficiency, no aortic stenosis (stenosis as defined by the orifice area of 1.5cm² or less), and no mural thrombus in the left ventricle)
- 2) Post-device removal – no later than 48 hours post-device removal; required for and the descriptive endpoint
- 3) 90 days post-device removal (\pm 30 days) – required for the analysis of the primary endpoint component (change in aortic insufficiency from baseline to 90 days) and the descriptive endpoint
- 4) Unscheduled – if new valvular abnormalities are suspected post device removal, an echocardiogram should be performed and the results documented on the eCRF.

Particular attention should be made to the presence of thrombus and any new abnormalities (or worsening of existing abnormalities) of the aortic valve.

IMPORTANT: All echocardiograms must have a focus on aortic valve (refer to the Echocardiographic Core Laboratory guidance) and must be submitted to the core laboratory for analysis. Both baseline and 90-day echocardiograms are required for the quantitative assessment of change in aortic insufficiency from baseline to 90 days, which is part of the primary endpoint in SHIELD II. For a baseline echocardiogram performed prior to the subject signing informed consent, the investigators will need to assess whether the available baseline echocardiogram captures the appropriate images of aortic valve required for a quantitative assessment of aortic regurgitation by the Echocardiographic Core Laboratory per the Echocardiographic Core Laboratory guidance. If not, a baseline echocardiogram will need to be repeated per the Echocardiographic Core Laboratory guidance before the index procedure.

Laboratory Assessments

The following laboratory assessments will be collected over the course of the clinical investigation. See **Table 2: Clinical Investigation Assessment Schedule** in **Section 6.9** for the required timing of these laboratory assessments.

Hematology:

Hemoglobin
Hematocrit
Red Blood Cells
White Blood Cells
Platelets

Cardiac Biomarkers:

Creatinine Kinase-MB (CK-MB)
Troponin (NO high-sensitivity troponin)

Hemolysis Biomarkers:

Plasma Free Hemoglobin (PfHgb)
Lactate Dehydrogenase (LDH)

Chemistries:

Aspartate Aminotransferase (AST)
Alanine Aminotransferase (ALT)
Total Bilirubin
Blood Urea Nitrogen (BUN)
Creatinine
Lactate
B-type Natriuretic Peptide (BNP) or NT-proBNP

Coagulation:

International Normalized Ratio (INR)
Activated Clotting Time (ACT)
Activated Partial Thromboplastin Time (APTT)/Partial Thromboplastin Time (PTT)

Physical Examination/Vital Signs

Physical examination will be completed and recorded at baseline, prior to hospital discharge, and at 90 days post-device removal. Any clinically significant findings during the physical examination should be reviewed by the investigator. Any clinically significant findings during the baseline physical examination should be reported in the subject medical history. Any clinically significant findings during physical examinations post-device insertion should be reported as adverse events. Physical examinations should be performed per the standard of care and may be completed by any qualified medical personnel.

Vital signs will be recorded at baseline, post procedure, and prior to hospital discharge.

Health Economics Data

Upon hospital discharge for the initial implant hospitalization and any subsequent rehospitalizations, redacted UB-04 bills (where it is applicable), or similar detailed

hospital billing data, will be requested to be entered into Abbott EDC. Duration of hospital stay and intensive care unit (ICU) duration will also be collected.

For rehospitalizations performed outside of the study center, clinical investigation staff should make their best effort to obtain the UB-04 bills (where it is applicable), or similar detailed hospital billing data and duration of stay information from the outside institution.

Concomitant Use of Anticoagulant and Antiplatelet Medications

The use of any oral anticoagulants, procedural anticoagulants, and post-procedural antiplatelet medications will be recorded.

6.9 Schedule of Events

The time windows and the schedule of the clinical investigation-required assessments are listed in **Table 1** and **Table 2**, respectively.

Table 1 – Time Windows for Select Clinical Investigation Assessments

Assessment	Time Window
Baseline Laboratory Testing (except for cardiac biomarkers)	Within 14 days prior to the index procedure
Baseline Cardiac Biomarkers: Both CK-MB and troponin (NO high-sensitivity troponin) are required.	Within 48 hours prior to the index procedure
Baseline 12-lead ECG	Within 48 hours prior to the index procedure
Baseline Echocardiogram	Within 60 days prior to the index procedure
Baseline Health Assessment and Quality of Life Questionnaires	Within 30 days prior to the index procedure
Diagnostic Angiogram	Within 60 days prior to the index procedure
Procedural Angiogram	During the index procedure
Pre-device Hemolysis Biomarkers	Before device insertion in the catheterization laboratory during the index procedure
Post-device Hemolysis Biomarkers	After device removal in the catheterization laboratory during the index procedure
Post-procedure Laboratory Testing (except for cardiac biomarkers)	Within 24 hours post device removal
Post-procedure Cardiac Biomarkers	
Both CK-MB and troponin (NO high-sensitivity troponin) are required for the post-procedural assessment:
 
 1. First draw at 6 to 12 hours post-device removal 2. If CK-MB is elevated $> 1x$ ULN or troponin is elevated $> 7x$ ULN in the first draw, a second draw of CK-MB and troponin is required at 18-24 hours post-device removal or at the time of discharge as long as discharge is at or after 16 hours post-device removal. 
Note: If CK-MB or troponin in the second draw is not stable and falling compared to the first draw, serial measurements of CK-MB and troponin every 12 hours or per site standard until a decline is noted are highly recommended.

Post-procedure 12-lead ECG	At least one within 24 hours post-device removal
Post-procedure Echocardiogram	Within 48 hours post device removal
90 Day Post-Device Removal Clinical Visit	\pm 30 days
90 Day Post-Device Removal Echocardiogram	\pm 30 days

Table 2 – Clinical Investigation Assessment Schedule

Clinical Test	Baseline ¹	Intraprocedure	Post-Procedure ¹⁰	Discharge	90 Days Post Device Removal	Unscheduled Visit
LABORATORY ASSESSMENTS						
Hemoglobin	X		X			
Hematocrit	X		X			
Red Blood Cells (RBC)	X		X			
White Blood Cells (WBC)	X		X			
Platelets	X		X			
Plasma Free Hemoglobin		X ¹⁵				
INR	X		X			
Activated Clotting Time (ACT)		X ¹⁶	X			
APTT/PTT	X		X			
Aspartate Aminotransferase (AST)	X		X			
Alanine Aminotransferase (ALT)	X		X			
Total Bilirubin	X		X			
Blood Urea Nitrogen (BUN)	X		X			
Creatinine	X		X			
Lactate Dehydrogenase (LDH)	X	X ¹⁵				
Creatine Kinase-MB (CK-MB)	X ²		X ¹¹			Optional
Troponin (NO high-sensitivity troponin)	X ²		X ¹¹			X ¹⁷
Lactate	X		X			
B-type Natriuretic Peptide (BNP) or NT-proBNP	X					
Pregnancy Test	X ³					
12-lead ECG						
12-lead ECG	X ⁴		X ¹²			X ¹⁷
Health Assessment & Quality of Life Questionnaires						
Euroscore II	X ⁵					
STS score	X ⁵					
NYHA Heart Failure Class	X ⁵				X	
Seattle Angina Questionnaire (SAQ)	X ⁵				X	
EQ-5D-5L	X ⁵				X	
IMAGING ASSESSMENTS						
Echocardiogram	X ⁶	X ⁹	X ⁹		X	X ¹⁸
Angiography Data	X	X				
HEMODYNAMIC ASSESSMENTS						
Hemodynamic Measurements (RAP/PAP/PCWP/CPO/CO/CI)		X ⁷				
MAP	X	X ⁸	X	X		
EXAMS						

Clinical Test	Baseline ¹	Intraprocedure	Post-Procedure ¹⁰	Discharge	90 Days Post Device Removal	Unscheduled Visit
Physical Examination	X			X	X	
Vital Signs	X		X	X		
Follow-up Clinic Visit					X ¹⁴	
Adverse Event Assessment		X	X	X	X	X ¹⁹
COVID-19 Assessment	X			X	X	X
Neurological Assessment					As required per event; See Section 6.7	
DEVICE ASSESSMENTS						
Pump Flow/Speed		X ⁸				
OTHER						
Health Economics Data					X ¹³	
Concomitant Use of Anticoagulant and Antiplatelet Medications	X	X	X	X	X	X

1. All baseline laboratory tests except for cardiac biomarkers must be done within 14 days prior to the index procedure.
2. Baseline cardiac biomarkers, including CK-MB and troponin (NO high-sensitivity troponin), must be assessed within 48 hours prior to the index procedure.
3. Pregnancy test is required for female subjects of childbearing potential within 14 days prior to the index procedure.
4. Baseline 12-lead ECG is required within 48 hours prior to the index procedure.
5. Health assessment and quality of life questionnaires must be done within 30 days prior to the index procedure.
6. Baseline echocardiogram must be done within 60 days prior to the index procedure. In addition to scheduled echocardiograms, echocardiograms should be performed any time new aortic valve abnormalities are suspected.
7. Hemodynamic assessments will be performed four times during the index procedure:
 - 1) Prior to device insertion
 - 2) Prior to the PCI procedure while on device support
 - 3) Immediately prior to weaning for the preparation of device shutdown and removal
 - 4) 10 to 30 minutes after device removal
8. The corresponding MAP for the same four time points and the corresponding pump speed and estimated pump flow for the time points 2) and 3) as specified above will be also collected during the index procedure. Blood pressure should be also collected at the time of inotrope/vasopressor administration.
9. Echocardiogram must be performed no later than 48 hours post-device removal. This can be done either during or after the index procedure.
10. Post-procedure laboratory assessments except for cardiac biomarkers must be done within 24 hours after device removal.
11. Both CK-MB and troponin (NO high-sensitivity troponin) are required for the post-procedural assessment:
 - 1) First draw at 6 to 12 hours post-device removal
 - 2) If CK-MB is elevated >1x ULN or troponin is elevated >7x ULN in the first draw, a second draw of CK-MB and troponin is required at 18-24 hours post-device removal or at the time of discharge as long as discharge is at or after 16 hours post-device removal.

Note: If CK-MB or troponin in the second draw is not stable and falling compared to the first draw, serial measurements of CK-MB and troponin every 12 hours or per site standard until a decline is noted are highly recommended.
12. At least one 12-ECG must be performed within 24 hours post device removal.
13. Upon hospital discharge for the initial index procedure hospitalization and for any subsequent re-hospitalization as described in Section 6.7.
14. Ninety-day Follow-Up Form is required even if subject is still hospitalized.
15. Pre-device (before device insertion) and post-device (after device removal) draws via vascular access sheath in the catheterization laboratory during the index procedure
16. ACT must be checked after giving procedural anticoagulant and must be ≥ 250 seconds prior to the wire/device insertion and throughout the procedure.
17. If an unscheduled visit is conducted due to a suspected ischemic cardiac event, troponin (NO high-sensitivity troponin) must be collected and ECG must be done. CK-MB is optional.
18. An echocardiogram should be performed if any new valvular abnormalities are suspected in the event of an unscheduled visit.
19. Details of any subsequent coronary interventions (e.g., repeat PCI or CABG) must be recorded, if applicable, in the event of an unscheduled visit.

6.10 Angiographic and Echocardiographic Core Laboratories

The clinical investigation will utilize an independent angiographic laboratory and an independent echocardiographic core laboratory for the assessment and evaluation of all angiograms and echocardiograms required during the clinical investigation period. The angiographic core laboratory will also calculate SYNTAX scores.

All clinical investigation-required angiograms and echocardiograms should be submitted to the core laboratories by uploading the assessments directly to the core laboratories' database.

7.0 ADVERSE EVENTS

To comply with worldwide standards and guidelines on clinical investigation adverse event reporting, the Sponsor has adopted uniform and worldwide applicable standard definitions and reporting timelines to be used and adhered to by the investigators.

7.1 Definition

7.1.1 Adverse Event

An adverse event (AE) is any untoward medical occurrence, unintended disease or injury, or untoward clinical signs (including abnormal laboratory findings) in subjects, users or other persons, whether or not related to the medical device under investigation.

Note 1: This definition includes events related to the medical device under investigation or the comparator.

Note 2: This definition includes events related to the procedures involved.

Note 3: For users or other persons, this definition is restricted to events related to medical devices under investigation.

7.1.2 Serious Adverse Event

If the AE meets any of the criteria below, it is regarded as a serious adverse event (SAE).

- a) Led to a death,
- b) Led to a serious deterioration in health of the subject, that either resulted in
 - 1. A life-threatening illness or injury, or
 - 2. A permanent impairment of a body structure or a body function, or
 - 3. In-patient hospitalization or prolongation of existing hospitalization, or
 - 4. Medical or surgical intervention to prevent life threatening illness or injury or permanent impairment to a body structure or a body function.

5. Chronic disease
- c) Led to fetal distress, fetal death or a congenital abnormality or birth defect.

Note: A planned hospitalization for pre-existing condition, or a procedure required by the protocol, without a serious deterioration in health, is not considered to be an SAE.

7.1.3 Device Deficiency

Device deficiency is defined as an inadequacy of a medical device related to its identity, quality, durability, reliability, safety or performance, such as malfunction, misuse or use error and inadequate labeling. This includes the failure of the device to meet its performance specifications or otherwise perform as intended. Performance specifications include all claims made in the labeling of the device.

7.2 Device Relationship

Determination of whether there is a reasonable possibility that an investigational product or device under investigation caused or contributed to an AE is to be **determined by the Investigator** and recorded on the appropriate CRF. Determination should be based on assessment of temporal relationships, evidence of alternative etiology, medical/biologic plausibility, and patient condition (pre-existing condition).

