2.2 Devices to Be Used in SHIELD II

2.2.1 Investigational Device

The investigational device is the HeartMate PHP System, consisting of a catheter pump and a catheter pump console, which are serial-controlled. The manufacturer is Thoratec Corporation at [name].

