6.3.2 Procedures Involved in the Use of the Study Device

HeartMate PHP and Impella are both temporary ventricular assist devices indicated for support during high-risk PCI. The study device (HeartMate PHP or Impella) will be inserted before the PCI procedure starts and will be removed after the PCI procedure ends. The preparation and use of the HeartMate PHP and Impella devices will be according to their respective IFUs.

HeartMate PHP and Impella device parameters will be collected and recorded on the appropriate electronic case report form (eCRF) in EDC. For the HeartMate PHP device, the data can be found on the console. For the Impella device, the data can be found on the automated Impella controller. All pump data collected should be kept in the patient binder.

If any issues occur with the use of the HeartMate PHP during the index procedure, the HeartMate PHP must be returned to Abbott after use. A device deficiency must be recorded as appropriate and as described in Section 7.3.3. After device removal in the catheterization laboratory, sites will record any gross device abnormalities (e.g., thrombus, cuts, tears, etc.) on the eCRF prior to shipment of the device to Abbott.

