15.2 Anticipated Potential Adverse Events

Risks associated with the HeartMate PHP and procedure, together with their likely incidence, are described in **Appendix IV**.

Anticipated potential adverse events associated with use of the HeartMate PHP are listed below:

- Aortic Insufficiency
- Aortic Valve Injury
- Bleeding
- Cardiac Arrhythmias
- Cardiogenic Shock
- Cardiac Tamponade
- Cerebrovascular Accident
- Death
- Device Malfunction
- Emergent Surgery
- Endocarditis
- Hemolysis
- Hepatic Dysfunction
- Hypertension
- Hypotension
- Insertion Site Infection
- Left Ventricular Perforation
- Limb Ischemia
- Myocardial Infarction
- Myocardial Ischemia
- Renal Dysfunction or Failure
- Respiratory Dysfunction
- Sepsis
- Thrombocytopenia
- Thromboembolism
- Transient Ischemic Attack
- Vascular Access Site and Access-related Complications and Vascular Injury

Anticipated potential adverse events associated with other procedures in this investigation beyond what is anticipated in high-risk PCI:

- Pulmonary Vasculature Injury (see **Section 15.4**)

There may be risks related to the device that are unknown at present. Likewise, the exact frequency of the risk may be unknown.

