2.12 Sensitivity Analysis

The following sensitivity analyses of the primary endpoint will be carried out:

Worst Case Scenario Analysis

Tipping Point Analysis

Statistical Analysis Plan

Multiple Imputation

3.0 **DESCRIPTIVE ENDPOINTS AND ADDITIONAL DATA**

Data in the feasibility phase of the clinical investigation will be analyzed separately from data in the pivotal phase of the clinical investigation. Data collected for both roll-in and randomized subjects will be summarized descriptively. The results of the roll-in cohort will be analyzed as adjunctive data, separate from the results of the randomized cohort.

3.1 **Baseline and Demographic Characteristics**

The following baseline and demographic variables will be summarized: gender, age, height, weight, baseline risk factors, medical history, morphology, quantitative coronary angiography, echocardiogram, implant procedural characteristics, device usage, and quality of life, etc.

3.2 **Adverse Events**

The start of the index procedure will be a reference start time for summarizing all adverse events. All of the adverse device effects, serious adverse device effects, UADEs will be summarized for all subjects who registered in this trial in terms the number of events and the percentage of subjects with events.

All CEC adjudicated adverse events will also be summarized for all subjects who registered in the trial by treatment arms in terms the number of events and the percentage of subjects with events.

Statistical Analysis Plan

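### Section 7.2 requires a relatedness judgement for HeartMate PHP only, leaving Impella-related and procedure-related effects without a required label while the SAP plans adverse-device-effect summaries for all registered subjects

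*Protocol*

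**What the plan says.** Protocol Section 7.2 assigns the relatedness decision to the investigator, to be recorded on the case report form. Its scope is "Determination of whether there is a reasonable possibility that an investigational product or device under investigation caused or contributed to an AE". No other object of the judgement is named.

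The protocol fixes what these terms mean. Section 2.2.1 states: "The investigational device is the HeartMate PHP System". The CIP Summary and Section 2.2.5 call Impella the control device. When both pumps are meant, Section 6.3.2 uses a different term: "The study device (HeartMate PHP or Impella) will be inserted before the PCI procedure starts".

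Section 7.1.1 is broader than 7.2. Its first note reads "This definition includes events related to the medical device under investigation or the comparator" and its second "This definition includes events related to the procedures involved".

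Section 6.3.1 makes right heart catheterization mandatory. Section 15.2 has a separate category, "Anticipated potential adverse events associated with other procedures in this investigation beyond what is anticipated in high-risk PCI", and lists pulmonary vasculature injury under it.

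SAP 3.2 plans that "All of the adverse device effects, serious adverse device effects, UADEs will be summarized for all subjects who registered in this trial". That sentence does not mention treatment arm; the next paragraph, on CEC-adjudicated events, does.

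**The concern.** The definition of an adverse event covers the investigational pump, the comparator and the procedures. The relatedness rule covers only the first of these. Read literally, it asks about a device that an Impella subject did not receive, so the answer cannot be yes. Nor does it ask whether the study-required catheter, rather than the pump or the PCI, caused an injury.

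The label matters because adverse device effects, serious adverse device effects and UADEs are defined by it, and the SAP plans to report them. The stated objective is safety and effectiveness compared with Impella. A table of device effects with one arm filled and the other empty by construction would mislead, and the error would count against the investigational device. Sites that extend the question to Impella on their own initiative would shrink the imbalance but make it depend on site habit. The trial is open-label, so labels reconstructed later would be both retrospective and unblinded.

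**Working it through.** The plan states no figure on this point, so the check is a comparison of texts.

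1. **Does the term in 7.2 include Impella?** Section 2.2.1 identifies the investigational device as HeartMate PHP. Section 7.1.1 sets the device under investigation and the comparator side by side as two different things. Section 6.3.2 has a collective term for the two pumps, and 7.2 does not use it. On the protocol's own vocabulary, 7.2 omits Impella.

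2. **Does other visible text require the Impella judgement?** Three places use wording that could cover either pump:
   - Section 7.2.1 defines unanticipated effects by reference to a device in general, but it covers only unanticipated serious problems.
   - Section 7.3.1 refers to devices in the plural, but only to say that all events are documented whatever the relationship.
   - Section 11.3 expects source records of the device-relationship assessment, but for serious events only.

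   None of them tells the investigator to judge Impella for adverse device effects in general.

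3. **Does any visible text ask for procedure relatedness?** None does, although 7.1.1 includes procedure-related events and 15.2 recognises a risk from study procedures beyond high-risk PCI.

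4. **Where does the label go?** SAP 3.2 summarizes device effects for all registered subjects. SAP 2.2.2 summarizes binary variables within treatment arm, permits rate differences, relative risks and p-values for events of interest, and has a denominator category that names adverse device effects (its content is redacted). A by-arm display is therefore a likely output, although 3.2 does not state one.

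5. **What would a literal reading do?** SAP 2.4 gives 315 PHP and 158 Impella subjects, 473 in total. The label could then not be given in 158/473 = 33.4% of the randomized cohort. If the true device-effect rate were r in both arms, the displayed rates would be r for PHP and 0 for Impella, a false difference of r. Pooled over the cohort, the displayed rate would be 315r/473 = 0.666r. The documents give no value for r, so these are statements of direction and form, not estimates.

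**The case against.** The strongest reply is that the form, not the sentence in 7.2, decides what investigators are asked. The form and the CEC charter were not supplied. The adverse event definitions in Appendix II, part of Section 15.4 and part of SAP 2.2.2 are redacted or not shown. The form may already ask about both pumps. This stands: the documents show a defect in the rule, not in the data.

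Several stronger readings are tempting and are not supported.

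- *Impella effects and catheter injuries are never attributed.* The visible text does not require attribution, which is a weaker statement. The events themselves are recorded in both arms under Section 7.3.1.
- *The safety comparison has no valid comparator.* SAP 3.2 summarizes CEC-adjudicated events by arm with no relatedness condition, and no component of the primary endpoint is defined by relatedness. In an open-label trial, all-cause and adjudicated rates are a better basis for comparing arms than investigator attribution.
- *The DSMB cannot judge PHP against Impella.* Section 10.8.2 has it review cumulative data. Its charter was not supplied, and nothing shows that it depends on this label.
- *Impella malfunctions go uncollected.* Section 6.3.2 does address only PHP when it begins "If any issues occur with the use of the HeartMate PHP during the index procedure". But Section 7.1.3 defines a device deficiency for a medical device generally, and Section 7.3.3 requires all deficiencies to be reported.
- *Roll-in and randomized subjects would be mixed.* SAP 3.0 already separates them.

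It can also be said that SAP 2.2.2 makes by-arm presentation the general rule. That is correct and makes the SAP change a clarification. It does not help with 7.2, because a by-arm table is where a one-sided label does its damage.

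**Conclusion.** The point holds as a mismatch between the relatedness rule, the adverse event definition and the planned summaries. In the protocol's own terms, 7.2 requires a judgement for HeartMate PHP only. If the adverse event form follows it literally, device effects are labelled in one arm and any by-arm display of them is biased against PHP. Injuries from the required catheterization also carry no label that separates them from effects of the pump or the PCI.

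This rests on one assumption that cannot be checked here, namely that the form follows the wording of 7.2. A reader might want a percentage-point size, but any such figure would only restate an assumed device-effect rate, and the documents supply none. What is affected is a descriptive safety summary. The primary non-inferiority test, the recording of events and the by-arm CEC summaries are untouched. The change is worth making because it is cheap and because attribution is best recorded when the event is reported.

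**What to change.** - In Section 7.2, replace the object of the judgement with *the study device used (HeartMate PHP or Impella)*.
- In the same section, add a separate relatedness judgement for the index procedure and for study-required procedures, including right heart catheterization.
- In SAP 3.2, add *by treatment arm* for the randomized cohort to the sentence on adverse device effects, serious adverse device effects and UADEs.

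The cost is a wording change in both documents and one or two extra fields on the adverse event form. If the form already asks these questions, only the wording changes. The labels remain unblinded investigator judgements, so the by-arm device-effect summary should be presented as descriptive only.
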